Establish and evaluate a rapid diagnostic service (Cepheid's Xpert® MTB/RIF) as a point of care test in the community to ensure suspected cases of TB in hard to reach groups are investigated promptly and optimally managed. This widely used polymerase chain reaction (PCR) based test detects the presence of *Mycobacterium tuberculosis* in sputum samples and identifies resistance to Rifampicin, a reliable surrogate marker of strains that are multidrug-resistant (MDR-TB).

Sub-study 5: Virtually Observed therapy (VOT) versus Directly Observed Therapy (DOT)

Individually randomised controlled trial comparing virtually observed therapy (VOT) arranged by a specialist community team using internet based technologies with standard directly observed therapy (DOT) arranged by a TB Service to support treatment adherence.

Sub-study 6: Cost effectiveness

Development of a dynamic transmission model to predict public health impact of the interventions and inform economic analysis comparing costs to the savings made through averting future cases.

STUDY PROCEDURES:

This programme is largely health services research and involves vulnerable and marginalised populations. Studies will be submitted for MREC approval.

The research studies will involve:

SUB-STUDY 1. Latent TB Infection (LTBI)

1. Primary objective:
 - To determine the prevalence of latent TB infection among prisoners, drug users and homeless people in London in order to inform a mathematical model (sub-study 6) of public health impact and cost effectiveness of screening (using IGRA testing) and treatment of LTBI among these hard to reach group.
2. Secondary objectives:
 - To determine the prevalence of co-infection with HIV, and hepatitis B and C in hard to reach groups in London and how this varies according to demographics and life style risk factors such as prison history, alcohol and drug use.
 - To measure the risk of progression from latent TB to active disease in hard to reach groups in London and how this varies according to demographics, co-infection with HIV, hepatitis B and C and other life style risk factors such as alcohol and drug user.

Setting:

1. HMP Pentonville prison will be the main site of recruitment for prisons. We may also include other prisons that are part of the Department of Health funded TB screening service who have established local arrangements for management of blood borne viruses, if necessary.

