LTBI Test Results	TB Referral		
	HIV positive	CXR Normal HIV negative	CXR Old HIV negative
Any positive IGRAs	TB Referral	Inform and advise	TB Referral
Indeterminate IGRAs	TB Referral	Inform and advise	TB Referral
All negative	No TB referral	No action	No action

BBV: Blood borne virus
 IGRAs: Interferon Gamma Release Assays
 LTBI: Latent TB (asymptomatic) infection

[figure not shown]
Economic evaluation: We will use the measured levels of latent TB infection, and blood borne viral infections, rates of progression to active TB, the results of previous studies on adherence and adverse reactions to chemoprophylaxis and the output of the mathematical model (study 6) to estimate potential public health impact and cost effectiveness of different approaches to screening and treatment for latent infection.

Duration and practical procedure: Testing will be conducted at the Royal Free Hospital (RFH) by the laboratory scientist employed for the study. The blood samples will be labelled with necessary patient identifiers as for clinical specimens and transported to the laboratory by the research nurse.

1. We will liaise closely with offender health services to coordinate testing to be around the same time routine X-ray screening is being performed. The prison screening will be completed by year 3 of the programme.

- Testing during the Health “MOT” sessions (alongside “Find&Treat” screening) will take place throughout the study and will be offered to all new and existing clients (extensive screening for blood born viruses is already conducted routinely by BBV teams working alongside the unit).

Sub-study 1

SUB-STUDY 2. Strengthening TB control in prisons

1. Primary objective: To determine the
 - Yield of screening and impact of infectiousness at diagnosis.
2. Secondary objectives: To measure
 - Prevalence of tuberculosis in those screened.
 - Screening coverage (proportion of eligible prisoners screened).
 - Diagnostic and treatment outcomes (including use of isolation resources, use of DOT, hospitalization and treatment completion) of people referred for investigation following an X-ray suggestive of active tuberculosis.
 - Future risk of tuberculosis.
 - Prevalence of old fibrotic lesion.

Setting: London prisons (Brixton and Pentonville) that are part of the Department of Health funded static digital X-ray programme for routine screening of prisons for TB.

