VOT Supervision	Research nurse will 
 - Observe the patients take their treatment through a video link between patients home and study office using a laptop with secure internet connection. - Provide on-going support i.e., weekly “face-to-face” internet chats to review patients’ status, clinically (e.g., side effects) and socially. 	N/A
Routine information collected	By research nurse 
 • Attendance • Doses taken • Side effects • Outcomes (diagnostic, treatment and clinical) • Loss to follow-up. 	By clinic specialist TB nurse 
 • Attendance • Doses taken • Side effects • Outcomes (diagnostic, treatment and clinical) • Loss to follow-up
Additional information collected	By research nurse 
 • Quality of life questionnaire (EQ-5D) • History of hospitalisation • History of sleeping rough • History of imprisonment. 	By clinic specialist TB nurse 
 • Quality of life questionnaire (EQ-5D) • History of hospitalisation • History of sleeping rough • History of imprisonment.
Incentives	The study will not provide financial incentives to attend VOT or DOT. However, participants in the VOT are allowed to keep the computer at the end of the study: and the clinic arm will retain flexibility to use incentives as is current practice.	

Sample size: Aim to recruit 400 patients (200 into each arm).

Participant follow-up procedure: In both arms a sputum sample will be collected 2 months into the treatment, and specimen cultured by the local microbiology laboratory to identify culture conversion (absence of viable organisms in the sputum). Data will be transferred to HPA for linkage to identify those who developed drug resistant TB and relapse case within 24 months of treatment completion.

Economic evaluation: We will compare the costs of delivering DOT in the clinic vs community VOT from an NHS perspective. The mathematical model will calculate the number of cases averted (including drug resistant cases) through improved adherence.

Duration and practical arrangements: This study will be completed by the end of year 4.

SUB-STUDY 6. Cost effectiveness.

1. Primary objective:
 - To determine the public health impact and cost effectiveness of the different interventions in sub-study 1 – 5.
2. Secondary objective:
 - None

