Setting: The model considers high-risk groups (homeless & prisoners) as well as the general population and will be generally applicable to TB control in low prevalence countries where TB is concentrated in hard-to-reach groups.

Target population: Homeless people, prisoners and general population at risk of TB in London.

Inclusion and exclusion criteria: Not applicable as this study relies on data analysis from sub-study 1-5.

Measurements: Most importantly, numbers of averted cases of infection, disease (improving health) and treatment (saving treatment costs) resulting from shortening (or preventing) the infectious period, and the most cost-effective combination of intervention elements in different settings. Other measures will include incidence and prevalence of latent infection. Changes over time will be reported as screening will initially increase numbers going on to treatment; subsequently, it will reduce them through averting infections. Benefits persisting in the decade beyond the end of the intervention will be calculated. Different intervention scenarios will be examined to determine the optimal strategy; sensitivity analysis will indicate the certainty of predictions.

Rates of progression in different groups are important epidemiologically, and having data on both the prevalence of latent infection and the prevalence of active disease in the same group will allow us to estimate them using the model.

Sample size: Aggregate data records from sub-study 1 - 5 will be used for this projected analysis.

Participant follow-up procedure: The model will be projected to 10 years beyond the end of the programme grant, i.e. 2023.

Economic evaluation: Output from the transmission model allows calculation of the cost per case treated and per case averted, taking into account reduced treatment costs through averting cases of infection and disease.

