Duration and practical arrangements: Mathematical modelling expertise is required at the start to ensure that the study collects data suitable for model parameter estimation. Then attention will turn to theoretical development and programming of the model (in the language, C++), including debugging, testing and validation, so that it is ready to use the empirical data when they become available. The most intense effort will be in the final years of the project, when data are available for model fitting, sensitivity analysis and examination of multiple different intervention scenarios to optimise the public health impact of IGRA / MXU screening and treatment. Computational analysis will use the high-performance computing cluster at Imperial College.

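### The cost-effectiveness model stops in 2023, which cuts off more of the benefit of treating latent infection than of X-ray screening, and no longer horizon is planned to show it

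*Protocol*

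**What the plan says.** The protocol's Sub-study 6 states under participant follow-up: "The model will be projected to 10 years beyond the end of the programme grant, i.e. 2023". Its measurements paragraph agrees: "Benefits persisting in the decade beyond the end of the intervention will be calculated". No longer or lifetime projection is mentioned. Sensitivity analysis is promised, but the horizon is not named among the inputs to be varied.

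That horizon serves every intervention. The primary objective of Sub-study 6 is "To determine the public health impact and cost effectiveness of the different interventions in sub-study 1 – 5", and one intended product is "the most cost-effective combination of intervention elements in different settings". The duration paragraph puts latent-infection testing and X-ray screening into the same search: "multiple different intervention scenarios to optimise the public health impact of IGRA / MXU screening and treatment". The economic output is defined by cases: "Output from the transmission model allows calculation of the cost per case treated and per case averted".

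Latent infection is not a side issue. The primary objective of Sub-study 1 is to inform the model about "cost effectiveness of screening (using IGRA testing) and treatment of LTBI among these hard to reach group", and its economic evaluation is to estimate "potential public health impact and cost effectiveness of different approaches to screening and treatment for latent infection".

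**The concern.** The options being compared have different time profiles. Testing and treating latent infection is paid for at once, while the active disease it prevents would have appeared gradually over the rest of life. X-ray screening finds people who are infectious now. The infections it averts are new ones, and part of the disease from new infections appears within a few years.

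A case prevented after 2023 counts for nothing in a cost per case averted that stops in 2023, and the treatment cost it would have saved is lost as well. If one option loses a larger share of its benefit than another, the comparison between them shifts for reasons of timing alone. The programme means to inform commissioning, so an order produced by the horizon could be read as a finding about the interventions.

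**Working it through.** **The plan's own figure.** Ten years back from 2023 puts the end of the grant in 2013. The protocol gives no grant end date against which to check this.

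**Inputs from the protocol.** The horizon is 10 years after the grant. Sub-study 2 runs for 4 years and Sub-studies 4 and 5 finish by the end of year 4, so an intervention modelled from the start of the programme could have a window of up to about 4 + 10 = 14 years.

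**Inputs assumed, because the protocol gives none.**
- Progression from remote latent infection, r: 0.1%, 0.5% or 1% a year.
- Loss or death, m: 1/40 or 1/20 a year.
- Discounting, d: 0 or 3.5% a year.
- After a new infection, 5% progress quickly at 0.5 a year and 95% behave like remote infection.
- Later generations of transmission are ignored for both options, and both clocks start together.

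**Formulas.** Write h = r + m + d and a = 0.5 + m + d.
- Slow cases per infection: lifetime S = r/h; within T years S(T) = S × (1 − e^(−hT)).
- Fast cases per infection: lifetime F = 0.05 × 0.5/a; within T years F(T) = F × (1 − e^(−aT)).
- Share kept, treatment of remote latent infection: 1 − e^(−hT).
- Share kept, X-ray screening: [F(T) + 0.95 S(T)] / [F + 0.95 S].

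**Largest tilt** (r = 0.001, m = 0.025, d = 0, T = 10).
- Latent infection: 1 − e^(−0.26) = 0.229.
- X-ray screening: (0.04737 + 0.95 × 0.00881) / (0.04762 + 0.95 × 0.03846) = 0.05574/0.08416 = 0.662.
- Ratio: 0.662/0.229 = 2.9.

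**Smallest tilt at 10 years** (r = 0.01, m = 0.05, d = 0.035).
- Latent infection: 1 − e^(−0.95) = 0.613.
- X-ray screening: (0.04261 + 0.95 × 0.06455) / (0.04274 + 0.95 × 0.10526) = 0.10393/0.14274 = 0.728.
- Ratio: 0.728/0.613 = 1.2.

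**All 24 scenarios: X-ray share kept divided by latent-infection share kept**

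| m | r | 10 y, d = 0 | 10 y, d = 3.5% | 14 y, d = 0 | 14 y, d = 3.5% |
|---|---|---|---|---|---|
| 1/40 | 0.1% | 2.89 | 1.88 | 2.29 | 1.55 |
| 1/40 | 0.5% | 1.66 | 1.41 | 1.44 | 1.26 |
| 1/40 | 1% | 1.35 | 1.24 | 1.24 | 1.15 |
| 1/20 | 0.1% | 2.06 | 1.58 | 1.68 | 1.34 |
| 1/20 | 0.5% | 1.47 | 1.30 | 1.30 | 1.18 |
| 1/20 | 1% | 1.27 | 1.19 | 1.17 | 1.11 |

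**Shares behind the 10-year columns.** Undiscounted, latent-infection treatment keeps 23-45% and X-ray screening 40-82%. At 3.5%, the figures are 46-61% and 63-91%.

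**If one fifth of those treated were recently infected,** latent-infection treatment keeps 30-59% undiscounted and 53-76% discounted at 10 years. The ratio is then 1.1 to 1.7.

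The direction is built into this structure. The X-ray share is a weighted average of a fast part, almost all kept (0.04737/0.04762 = 99% in the first example), and the same slow part that latent-infection treatment has. The calculation therefore informs mainly about size.

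**The case against.** Three stronger readings are tempting, and the document supports none of them.

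- A reader might infer that the cut-off takes little from X-ray screening. Sub-study 6 itself says that screening first raises the number on treatment and reduces it only later, through averted infections. Under the assumptions above, X-ray screening loses 18-60% of its lifetime averted cases undiscounted and 9-37% at 3.5%. The modelled benefits of rapid diagnosis and virtually observed therapy also include averted infections or cases, so they are not untouched either.
- A reader might take the truncation of latent-infection benefit alone as the tilt. A constant hazard over 40 years keeps 10/40 = 25%, a 4-fold loss. A hazard halving every 5 years over 30 years keeps 0.75/(1 − 0.5^6) = 76%, a 1.3-fold loss. Ranking depends on what both options keep, and no scenario above reaches 4.
- A reader might conclude that the order of interventions would reverse. The protocol gives no costs, progression rates or discount rate, so this cannot be shown.

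Other points also have force. A stated 10-year horizon is a choice, not a contradiction. The window may exceed 10 years, and the protocol expects higher progression risk in these groups; both shrink the tilt. The plan also reports changes over time, infections averted, the prevalence of latent infection and several scenarios. The remaining latent reservoir would therefore be partly visible, and nothing bars the horizon from the sensitivity analysis.

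These points reduce the size and the severity. They do not remove the point, because no output that ends in 2023 can show cases averted after 2023, and the horizon is fixed in the text rather than left open.

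**Conclusion.** The point holds as a moderate weakness in a stated analysis choice. One horizon ending in 2023 is used to compare options whose benefits arrive at different times. It removes benefit from both X-ray screening and latent-infection treatment, and more from the latter.

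X-ray screening keeps about 1.2 to 2.9 times the share that latent-infection treatment keeps at 10 years, and about 1.1 to 2.3 times with a 14-year window. If intervention costs fall at the start and treatment savings are set aside, the same factor distorts the relative cost per case averted. All of this rests on assumed progression, loss and discount rates, and on a simple model without onward generations of transmission. The measure is cases averted; counted in infections averted, X-ray screening would lose less. Confidence in the direction is reasonable, confidence in the size is low, and the effect on ranking is unknown.

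**What to change.** Keep the projection to 2023 as planned. Add to Sub-study 6, before results are available, a second and longer horizon (for example 30-40 years, or lifetime) as a named sensitivity analysis. Report cost per case averted and the ranking of interventions under both horizons, and flag any order that depends on the horizon. State the start of the modelled window and the discount rate, since both alter the size of the effect.

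Lifetime is the cleaner choice if progression proves slow. In the largest-tilt scenario, 40 years still keeps only 1 − e^(−1.04) = 65% of latent-infection benefit. X-ray screening then keeps (0.04762 + 0.95 × 0.03846 × 0.647)/0.08416 = 85%, so the ratio falls from 2.9 to 1.3.

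The cost is additional runs on the computing cluster already planned, with no new participants or data. The downside is that long projections are more uncertain, which reporting both horizons side by side makes visible.
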